### Missing data

Missing data will be handled implicitly by the mixed model for the main analyses (Table 2). Incomplete outcome data, for example, caused by patients missing some visits or dropping out of the study, are common in longitudinal studies. Mixed models assume that the missingness is independent of unobserved measurements, but dependent on the observed measurements. This assumption is called “*Missing At Random*” (MAR) and is often reasonable. Using mixed models, valid estimates of treatment effects will be obtained even when the missing values are not completely random (“*Missing Completely At Random*”, [MCAR]) and additional methods for handling missing data, such as multiple imputation, are generally not required.

Missing data have until recently, seriously compromised inferences from clinical trials. For example, editorials in the New England Journal of Medicine have noted how missing data have limited the ability to draw definitive conclusions from weight-loss trials. Analyses that are performed with methods such as repeated measures mixed models often assume that missing data are missing at random (MAR), and such an assumption often makes sense for the primary analyses. However, the observed data can never verify whether this assumption is correct. Therefore, we will assess robustness by using sensitivity analyses, noting that explicit use and reporting of sensitivity analyses is a novel area in trial research; i.e. the interpretation of the collective results from a sensitivity analysis when some of the analyses are in opposition to the primary analysis are not without controversies. However, we will assess the robustness of inferences (from our primary analyses) about treatment effects to various missing-data assumptions by conducting sensitivity analyses that relates inferences to one or more parameters that capture departures from the primary missing data assumption.

Sensitivity analyses should be easy to interpret by clinicians. We will apply the framework suggested by White et al, published in the British Medical Journal (2011) for intention to treat analysis that depends on making plausible assumptions about the missing data and including all participants in sensitivity analyses:

1. We did our best to follow up all randomized participants, even if they withdrew from their allocated treatment (i.e. real data is better than statistical imputation strategies).
2. We will perform a main analysis of all observed data that are valid under a plausible assumption about the missing data by using repeated measures mixed linear models (valid assuming that data is '*Missing At Random*'); See Table 2.
3. We will perform sensitivity analyses to explore the effect of departures from the assumption made in the main analysis; see SAP-Appendix Tables 1 and 2.

4. We will account for all randomized participants, also in the sensitivity analyses:

- We will apply a “non-responder imputation techniques” for the missing data (using BOCF) in the analyses provided in SAP-Appendix Table 1 (potentially valid even if data is '*Not Missing At Random*' [NMAR]).
- We will apply a naïve approach where we only perform our analyses on the data set where participants with missing data is excluded; i.e. participants with complete data for all of the four outcomes while still respecting the original treatment allocation (i.e. valid assuming data is Missing Completely at Random; MCAR), and using simple two-sample t-tests; see SAP-Appendix Tables 2.

If the treatment effect is qualitatively maintained for the range of offsets that are clinically plausible, then the findings will be considered robust. Extensions apply the offsets to means adjusted for available covariates (e.g. stratifying factors).

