### Change from baseline

|                               | Outcome            | ID
(n=XX) | CD
(n=XX) | Difference (95%CI) | P-
value |
|-------------------------------|--------------------|--------------|--------------|--------------------|-------------|
| Primary outcome        | Weight loss, kg    |              |              |                    |             |
| Key secondary outcomes | Serum urate, mg/dL |              |              |                    |             |
|                               | VAS fatigue        |              |              |                    |             |
|                               | VAS pain gout      |              |              |                    |             |

Values are least squares means (SE), unless otherwise stated. Abbreviations: ID – intensive diet, CD – conventional diet.

1: Continuous outcome estimates will be derived from the repeated measures linear mixed models where missing data in the ITT population is handled explicitly with a non-responder imputation (i.e. baseline observation carried forward; indicative of a possible NMAR issue); the inference will be provided as the difference between least squares means with 95% CI's around them.

**SAP-Appendix Table 2:** Changes in primary and key secondary endpoints (using 2-sample t-tests)

|                               |                    | Change from baseline  |              |                    |         |
|-------------------------------|--------------------|-----------------------------------|--------------|--------------------|---------|
|                               | Outcome            | ID
(n=XX)                      | CD
(n=XX) | Difference (95%CI) | P-value |
| Primary outcome        | Weight loss, kg    |                                   |              |                    |         |
| Key secondary outcomes | Serum urate, mg/dL |                                   |              |                    |         |
|                               | VAS fatigue        |                                   |              |                    |         |
|                               | VAS pain gout      |                                   |              |                    |         |

Values are means (SD). Abbreviations: ID – intensive diet, CD – conventional diet.

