1: Continuous outcomes estimates will be derived from descriptive statistics and 2-sample t-tests (change from baseline at 16 weeks) where missing data is handled explicitly by excluding participants with missing data for any of the four outcomes while still respecting the original treatment allocation (i.e. valid assuming data is missing completely at random); the inference will be provided as the difference group means with 95% CI's around them.

**SAP-Appendix Table 3:** Changes in primary and key secondary endpoints (adjusted for the three stratifying factors)\*

|                               |                    | Change from baseline  |              |                    |         |
|-------------------------------|--------------------|-----------------------------------|--------------|--------------------|---------|
|                               | Outcome            | ID
(n=XX)                      | CD
(n=XX) | Difference (95%CI) | P-value |
| Primary outcome        | Weight loss, kg    |                                   |              |                    |         |
| Key secondary outcomes | Serum urate, mg/dL |                                   |              |                    |         |
|                               | VAS fatigue        |                                   |              |                    |         |
|                               | VAS pain gout      |                                   |              |                    |         |

Values are least squares means (SE), unless otherwise stated. Abbreviations: ID – intensive diet, CD – conventional diet.

\*Based on the same statistical model as the primary analyses (Table 2); adding three further covariates corresponding to the stratified analysis.

1: Continuous outcome estimates will be derived from the repeated measures linear mixed models where missing data in the ITT population is handled explicitly with a non-responder imputation (i.e. baseline observation carried forward); the inference will be provided as the difference between least squares means with 95% CI's around them.

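### The SAP's robustness rule needs a range of offsets, but neither designated sensitivity table varies an offset, so the rule cannot be applied to the planned analyses

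*SAP*

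**What the plan says.** The main analysis is a repeated-measures mixed model that assumes data are missing at random (MAR). The Missing data part of SAP Section 6 accepts that the observed data cannot verify this. It promises "sensitivity analyses that relates inferences to one or more parameters that capture departures from the primary missing data assumption".

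Item 3 of the numbered list names the tables that will do this. They are to "explore the effect of departures from the assumption made in the main analysis; see SAP-Appendix Tables 1 and 2". Item 4 adds: "We will account for all randomized participants, also in the sensitivity analyses".

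The section then states the decision rule: "If the treatment effect is qualitatively maintained for the range of offsets that are clinically plausible, then the findings will be considered robust". One further sentence extends the offsets to covariate-adjusted means, again without values.

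The table footnotes say how missing data are treated:
- Appendix Table 1: "handled explicitly with a non-responder imputation (i.e. baseline observation carried forward; indicative of a possible NMAR issue".
- Appendix Table 2: two-sample t-tests after "excluding participants with missing data for any of the four outcomes while still respecting the original treatment allocation", described as valid if data are missing completely at random (MCAR).
- Appendix Table 3 (adjustment for the stratifying factors, not listed in item 3): the asterisk note says "Based on the same statistical model as the primary analyses (Table 2", but footnote 1 says missing data are "handled explicitly with a non-responder imputation (i.e. baseline observation carried forward".

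The protocol's Statistical methods section refers to a pre-established SAP and contains no missing-data sensitivity plan of its own.

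**The concern.** The rule calls for a set of analyses along a scale of departure from MAR, a clinically plausible stretch of that scale, and a criterion for the effect having survived. The SAP supplies none of these. It gives no value, unit or range for the offset, does not say which arm or arms receive it, and does not say whether maintained refers to the sign or to the confidence interval.

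The two designated tables do not fill the gap. Carrying the baseline forward is one departure, whose size is set by the observed data and whose direction is the same in both arms. The complete-case analysis assumes MCAR, which is stricter than MAR, so it does not probe departures in the direction that matters. It also drops participants, contrary to item 4.

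What is at stake is the robustness statement. As the plan stands, the findings could be called robust without the analysis that the rule requires, and the criterion could be settled after the results are known. The SAP itself says that missing data have limited the conclusions of weight-loss trials.

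**Working it through.** **Inputs.** From SAP Section 3, Power and sample size: difference 5 kg, SD of change 6.0 kg, 30 per arm, dropout up to 20% (6 per arm, 24 observed). From SAP Section 4: two-sided 5%. Assumed for scale: a loss of 12 kg in the intensive diet (ID) arm, which is the protocol's 8-week figure from an earlier knee osteoarthritis study, and 12 - 5 = 7 kg in the conventional diet (CD) arm. Positive values are kg lost.

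**The plan's own figures.** Two-sample t-test power (noncentral t) is 0.8876 at 30 per arm (stated 0.888) and 0.8068 at 24 per arm (stated above 0.80). Both reproduce.

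**Main analysis at 20% missing.** SE = 6 x sqrt(2/24) = 1.732; t(46) = 2.013; half-width 3.486. The 95% CI is 5 ± 3.486, or 1.51 to 8.49.

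**Offsets.** Let d be how much less the missing ID patients lost than MAR predicts, and f the missing fraction. With an offset in ID only, the estimate is 5 - f x d.
- Sign reversal: d = 5/0.20 = 25 kg.
- CI first includes zero, SE held constant: (5 - 3.486)/0.20 = 7.57 kg.
- The same, with f(1 - f)d²/30 added to the variance: 6.85 kg. Check: 5 - 0.2 x 6.85 = 3.63, and 2.013 x sqrt(3 + 0.16 x 6.85²/30) = 3.63.

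Baseline adjustment is approximated by multiplying the SE by sqrt(1 - r²), where r is an assumed correlation of baseline with change.

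| Missing per arm | MAR difference | r | CI includes zero at (SE constant / added variance) | Sign reverses at |
|---|---|---|---|---|
| 20% | 5 kg | 0 | 7.57 / 6.85 kg | 25 kg |
| 20% | 5 kg | 0.3 | 8.37 / 7.48 kg | 25 kg |
| 20% | 5 kg | 0.5 | 9.90 / 8.63 kg | 25 kg |
| 10% | 5 kg | 0 | 17.23 / 13.86 kg | 5/0.10 = 50 kg |
| 30% | 5 kg | 0 | 4.19 / 3.99 kg | 5/0.30 = 16.7 kg |
| 20% | 7 kg | 0 | 17.6 / 14.5 kg | 7/0.20 = 35 kg |

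The 30% row is above the plan's upper dropout figure.

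With opposite offsets in the two arms at 20% missing, the estimate is 5 - 0.4d. The CI includes zero at 3.78 kg (SE constant) or 3.59 kg (added variance), and the sign reverses at 5/0.40 = 12.5 kg. With equal offsets in the same direction and equal dropout, the estimate is 5 - 0.2d + 0.2d = 5.0 kg, so there is no sign reversal.

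**What the baseline-carried-forward table shows.** At 20% missing in each arm: 0.8 x 12 - 0.8 x 7 = 4.0 kg, SE 1.723, 95% CI 0.55 to 7.45, p = 0.024. With equal dropout the estimate is always (1 - f) times the observed difference, so its sign cannot change whatever the missing patients did. With unequal dropout it does react: at 30% ID and 20% CD it is 0.7 x 12 - 0.8 x 7 = 2.8 kg (-0.72 to 6.32). It is one point in each case. Its implied offset equals the arm's mean change only if MAR predicts that mean for the dropouts.

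**Urate.** With 1.2 mg/dL, SD 1.6 and 20% missing, SE = 0.462. An ID-only offset brings zero into the CI at 1.35 mg/dL (SE constant) or 1.26 mg/dL (added variance); the sign reverses at 1.2/0.20 = 6.0 mg/dL.

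All SEs are two-sample approximations to the repeated-measures model and do not use the week-8 data.

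**The case against.** The best defence is that a genuine not-missing-at-random analysis is planned and labelled as such, and that it responds to heavier dropout in the intensive arm. The SAP works at two-sided 5%, speaks of the robustness of inferences, and gives both sensitivity tables a CI and a P-value column, so the CI is the natural reading of maintained. It also cites a published framework for intention-to-treat analysis with missing outcomes. In a 60-patient proof-of-concept trial a large grid of scenarios would be heavy.

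Much of this stands. The criterion is less open than the range, and the remedy should be small. It does not supply the missing part: a citation cannot give trial-specific limits in kg, mg/dL or mm, and one departure is not a range.

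Three stronger readings are tempting, and the documents do not support them.
- A reader might infer that departures from MAR are ignored, or that the primary result is unsound. Appendix Table 1 is such a departure, and no primary analysis depends on the rule.
- A reader might infer that the same data could in general be called robust or not at will. The split between sign and CI over 0 to 12 kg appears for a 5 kg difference at 20% missing. It does not appear at 10% missing, or for a 7 kg difference at 20%.
- A reader might infer that carrying the baseline forward conceals a lost result, because allowing for imputation uncertainty at the same point gives a CI of -0.04 to 8.04 (SE sqrt(3 + 0.16 x (12² + 7²)/30) = 2.007). With r = 0.3 the SE is sqrt(3 x 0.91 + 1.03) = 1.94 and the CI is about 0.1 to 7.9, so the contrast disappears.

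**Conclusion.** The point holds as one about the robustness rule. That the rule and the designated tables do not match follows from the SAP text alone and needs no assumption. The primary test, estimate, power and testing hierarchy are untouched.

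The size is illustrative. With a 5 kg difference, SD 6 kg, 20% missing per arm and an ID-only offset, the CI criterion fails at about 7 to 10 kg and the sign criterion at 25 kg. Where dropout is lower or the effect larger, the choice of criterion makes no difference over 0 to 12 kg. The omission therefore matters most if dropout approaches the plan's upper figure or differs between arms. It should be corrected, but it is no threat to the primary result.

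**What to change.** Before the data are analysed, add one delta-adjusted (pattern-mixture) appendix table, for body weight at least and preferably for all four hierarchically tested outcomes.

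1. Impute week 16 under the primary MAR model, including the week-8 data.
2. Add offsets to the imputed values in ID only, and in both arms with unequal or opposite offsets.
3. Fix the clinically plausible range in advance as numbers (kg, mg/dL or mm), with its rationale, so that it does not depend on the observed change.
4. State that maintained means the 95% CI still excludes zero. Report the tipping point where one exists, and sign reversal as supportive.
5. Keep the baseline-carried-forward and complete-case tables as supportive, and correct item 4, since the latter excludes participants.

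The cost is a paragraph, a table and modest programming, with no new data and no change to the primary test or sample size. The downside is a possibly less favourable robustness statement.

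The minimum alternative is to delete the offset sentence and state in advance how Appendix Tables 1 and 2 will be judged. This removes the contradiction but leaves no range of departures examined.

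Separately, reconcile the two notes to Appendix Table 3: one claims the primary model, in which missing data are handled implicitly, and the other names baseline carried forward.

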### Harms and adverse events

The number (and percentage) of patients experiencing any AE/SAE will be presented for each treatment group including gout flares.

### Statistical software

The analysis will be carried out using SAS Studio and R version 3.6.0 (or newer).

## Proposed outline of tables and figures:

**Figure 1: CONSORT flow diagram**

[figure not shown]
**Table 1:** Baseline characteristics

| Baseline characteristics               |              |              |                  |
|--|--------------|--------------|------------------|
| Variables                              | ID
(n=XX) | CD
(n=XX) | Total
(n=XXX) |
| Age, years                             |              |              |                  |
| Male sex, n(%)                         |              |              |                  |
| Ethnicity (Caucasian), n(%)            | 100%         | 100%         | 100%             |
| Body weight, kg                        |              |              |                  |
| BMI, m/kg                  |              |              |                  |
| BMI $\geq 40$ kg/m  , n(%) |              |              |                  |
| Duration of gout, years                |              |              |                  |
| Serum urate, mg/dL                     |              |              |                  |
| Serum urate $\geq 6$ mg/L, n(%)        |              |              |                  |
| Presence of palpable tophi, n(%)       |              |              |                  |
| Comorbidity:                           |              |              |                  |
| Kidney stones, n(%)                    |              |              |                  |
| Gall stones, n(%)                      |              |              |                  |
| Cardiovascular disease, n(%)           |              |              |                  |
| Diabetes, n(%)                         |              |              |                  |
| Hypertension, n(%)                     |              |              |                  |
| Hyperlipidemia, n(%)                   |              |              |                  |
| Any urate lowering therapy, n(%)       |              |              |                  |
| Any anti-inflammatory medication:      |              |              |                  |
| Colchicine, n(%)                       |              |              |                  |
| NSAID, n(%)                            |              |              |                  |
| Prednisone, n(%)                       |              |              |                  |
| Outcome Measures:                      |              |              |                  |
| VAS fatigue, 0-100 mm                  |              |              |                  |
| VAS pain gout, 0-100 mm                |              |              |                  |
| VAS pain global, 0-100 mm              |              |              |                  |
| HAQ                                    |              |              |                  |
| Swollen joint count                    |              |              |                  |
| Tender joint count                     |              |              |                  |

[figure not shown]
|                         |  |  |  |
|-------------------------|--|--|--|
| Palpable tophi,         |  |  |  |
| SF 36 MCS, 0-100 points |  |  |  |
| SF 36 PCS, 0-100 points |  |  |  |

Values are means (SD), unless otherwise stated. Abbreviations: ID – Intensive diet, CD – Conventional diet.

**Figure 2A:** Weight in kg among the two groups

**Figure 2B:** Serum urate in mg/dL among the two groups (ABS)

From the Linear Mixed Models, the Least Squares Means estimates will be based on our primary statistical model(s). Values will be illustrated as the absolute value (i.e. not change from baseline which will be used for Table 2). Error Bars will – in the final figure - illustrate the standard error for the least squares means. The dashed line illustrates the treatment goal for non-tophous gout 6mg/dL. Abbreviations: ID – intensive diet, CD – conventional diet.

**Table 2:** Changes in primary and secondary endpoints

|                          | Change from baseline  |              |              |                       |         |
|--------------------------|-------------------------------------|--------------|--------------|-----------------------|---------|
|                          | Outcome                             | ID
(n=XX) | CD
(n=XX) | Difference
(95%CI) | P-value |
| Primary outcome          | Weight loss, kg                     |              |              |                       |         |
| Key secondary outcomes   | Serum urate, mg/dL                  |              |              |                       |         |
|                          | VAS fatigue                         |              |              |                       |         |
|                          | VAS pain gout                       |              |              |                       |         |
| Other secondary outcomes | On treatment target, n(%)*          |              |              |                       | n.a.    |
|                          | Serum urate reduction, %            |              |              |                       | n.a.    |
|                          | VAS patient global                  |              |              |                       | n.a.    |
|                          | HAQ                                 |              |              |                       | n.a.    |
|                          | Swollen joint count                 |              |              |                       | n.a.    |
|                          | Tender joint count                  |              |              |                       | n.a.    |
|                          | Palpable tophi                      |              |              |                       | n.a.    |
|                          | SF-36 MCS                           |              |              |                       | n.a.    |
|                          | SF-36 PCS                           |              |              |                       | n.a.    |

Abbreviations: ID - Intensive diet, CD – conventional diet.

1: Continuous outcome estimates will be derived from the repeated measures linear mixed models where missing data in the ITT population is handled implicitly; the inference will be provided as the difference between least squares means with 95 CI's around them.

2: Dichotomous outcomes will be reported directly as observed (no imputations); the inference will be provided (unadjusted as the difference between proportions, i.e. Risk Difference, with 95% confidence interval).

\*Defined as having a serum urate < 6.0 mg/dL at both week 8 *AND* week 16

**Table 3:** Adverse events and harms

| Event                              | ID
(n=XX) | CD
(n=XX) | Difference (95%CI) |
|------------------------------------|--------------|--------------|--------------------|
| Self-reported flare, 0-16 weeks    |              |              |                    |
| First 8 weeks (0-8)                |              |              |                    |
| Last 8 weeks (8-16)                |              |              |                    |
| Other                              |              |              |                    |
| Serious Adverse Events, 0-16 weeks |              |              |                    |
| Death                              |              |              |                    |

Abbreviations: ID - Intensive diet, CD – conventional diet.

These dichotomous adverse outcomes will be reported directly as observed (no imputations) with number and percentages; the inference will be provided (unadjusted) as difference between proportions (i.e. Risk Difference, with 95% confidence interval).

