## Objectives

Primary efficacy objective: To compare the effect of intensive weight loss, relative to the control group, on changes in body weight from baseline to week 16, in patients with gout and concomitant obesity.

Key secondary efficacy objectives: To compare the effect of intensive weight loss, relative to the matched control group, on changes in serum urate, changes in VAS-fatigue, and changes in VAS-Pain from baseline to week 16, in patients with gout and concomitant obesity.

Other secondary objectives: To explore the effect of the intensive weight loss, relative to the matched control group, on all the following exploratory secondary outcomes:

- proportion of participants maintaining serum urate levels <6mg/dL at visit week 8 and week 16
- percentage reduction in serum urate (%) at final visit (week 16)
- the proportion of individuals with any gout flare in the FIRST 8 weeks following randomization
- the proportion of individuals with any gout flare in the LAST 8 weeks following randomization
- the number of gout flares during the trial period for each patient (up to week 16)
- change in functional status (HAQ) from baseline to week 16
- change in patient global (VAS) from baseline to week 16
- change in swollen joint count (SJC) from baseline to week 16
- change in tender joint count (TJC) from baseline to week 16
- change in number of tophi from baseline to week 16
- change in 36-Item Short Form Health Survey SF-36: Mental Component Scale (MCS) from baseline to week 16
- change in 36-Item Short Form Health Survey SF-36: Physical Component Scale (PCS) from baseline to week 16.

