| Concurrent medication:              |                                  |                     |                         |                      |  |
| Diuretics y/n                              |                                  | X                   |                         |                      |  |
| Aspirin y/n                                |                                  | X                   |                         |                      |  |
| Antihypertensive medication y/n            |                                  | X                   |                         |                      |  |

|   |  |   |   |   |
|---|--|---|---|---|
| Lipid lowering agents y/n                                 |  | X |   |   |
| Diabetes medication y/n                                   |  | X |   |   |
| Blood tests (lab. work):†                          |  |   |   |   |
| Creatinine, mg/dL   |  | X | X | X |
| eGFR, mL/min/1.73m                            |  | X | X | X |
| Serum urate, mg/dL  |  | X | X | X |
| Physical examination (Nurse):                      |  |   |   |   |
| Flares* in the last 8 weeks, count                        |  | X | X | X |
| Body weight, kg   |  | X | X | X |
| Touch screen (PROMs):                              |  |   |   |   |
| SF-36 health survey, score                                |  | X | X | X |
| Activity limitation (HAQ), score                          |  | X | X | X |
| Pain (VAS), mm  |  | X | X | X |
| Patient global (VAS), mm                                  |  | X | X | X |
| Fatigue (VAS), mm   |  | X | X | X |
| Physical examination (MD):                         |  |   |   |   |
| ACR/EULAR gout classification                             |  | X |   |   |
| Gout according to expert opinion                          |  | X |   |   |
| Swollen joint count, 0-66                                 |  | X | X | X |
| Tender joint count, 0-68                                  |  | X | X | X |
| Palpable tophi count                                      |  | X | X | X |
| Randomisation (after confirming written informed consent) |  | X |   |   |
| Harms and adverse events‡ (AEs):                   |  |   |   |   |
| Withdrawal, y/n   |  |   | X | X |
| Withdrawal due to AEs, y/n                                |  |   | X | X |
| Number of serious adverse events, count                   |  |   | X | X |
| Death, y/n  |  |   | X | X |

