#### *Other Secondary Outcomes:*

The proportion of participants reaching and maintaining target SU levels, defined as 8 weeks and 16 week visits with SU<6 mg/dL, respectively; the percentage reduction in SU at final visit (week 16); the proportion of individuals with any gout flare in the first-, and last 8 weeks following randomization, respectively; the number of gout flares during the trial period for each patient; functional status (HAQ); patient global (VAS); swollen joint count (SJC); tender joint count (TJC); change in number of tophi from baseline; and 36-Item Short Form Health Survey (SF-36: MCS and PCS apply).

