### Analysis methods

For the primary and key secondary outcomes, we will use analysis of covariance (ANCOVA) modelled using repeated-measures mixed linear model analysis. Statistical tests inferring from P-values will be performed in sequence until one of the analyses has failed to show the significant difference or all analyses have been completed at a significance level of 0.05. The sequence of the analyses for the selected secondary efficacy endpoints are listed as: (1) Change in body weight; (2) Change in serum urate; (3) Change in VAS Fatigue. (4) Change in VAS Pain. The statistical model will include diet group (ID/CD) and time (in weeks) as fixed effects, and the interaction between time and diet group, with the respective variable (e.g. body weight at baseline) as covariate. Furthermore, the possible impact of the factors used for the stratified randomization will be explored, i.e. sex (M/ F), obesity class (<40/≥40 kg/m^2), and SU level (< 6/≥6 mg/dL) but will not be considered part of the primary model. We aim to assess whether data provide evidence of superiority of ID to CD group (primary objective). Thus, the null hypothesis is no difference

between treatments at endpoint (week 16). Response variables and adverse events (binary outcomes) will be analyzed by comparing the proportions responding in each group with the Risk Difference (and 95% CI's), with no further adjustments for covariates.

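### Does the number of gout flares per patient need its own analysis method and table row in the SAP?

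*SAP*

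**What the plan says.** SAP Section 2 (Objectives) and Section 6 (Other Secondary Outcomes) both list "the number of gout flares during the trial period for each patient", separately from the proportions with any flare in the first and the last 8 weeks. Objectives labels the whole list exploratory. The schedule under Timing of outcome assessments has the nurse record "Flares* in the last 8 weeks, count" at baseline, week 8 and week 16.

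SAP Analysis methods names two approaches. The primary and key secondary outcomes get a repeated-measures mixed linear model with group, time and their interaction. For binary outcomes it says: "Response variables and adverse events (binary outcomes) will be analyzed by comparing the proportions responding in each group with the Risk Difference". Note 1 to Table 2 extends the mixed model to the continuous outcomes in that table.

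Table 3 has three flare rows, headed by "Self-reported flare, 0-16 weeks" and followed by the two 8-week halves. Its note reads: "These dichotomous adverse outcomes will be reported directly as observed (no imputations) with number and percentages". The Harms section likewise counts patients with any event. The missing-data text concerns the mixed model, and the appendix tables cover only the four tested endpoints.

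**The concern.** A listed outcome without a row or a method invites one of two results: it goes unreported, or the method is chosen after the data are seen. Flares matter clinically here. The protocol's review of earlier studies mentions one bariatric-surgery study with a temporary rise in the number of flares, and its Harms section treats each flare as an adverse event. A yes/no row cannot show several flares in one patient. A total over 16 weeks is also incomplete when the second 8-week count is missing, and adding up what was seen would treat 8 weeks as 16. The sample-size section itself allows for 6 drop-outs per group.

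**Working it through.** The documents give no flare rate, dispersion or power for flares, so there is no figure of the plan's own to reproduce. The check is a reading of the text, followed by illustrations on assumed counts.

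**1. Outcomes against table rows.** SAP Objectives lists 12 other secondary outcomes.
- Table 2 rows: SU target, percentage SU reduction, patient global, HAQ, swollen joints, tender joints, tophi, SF-36 MCS and SF-36 PCS, which is 9.
- Table 3 rows: any flare in the first and in the last 8 weeks, which is 2.
- Number of flares: 0.

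So 9 + 2 = 11 of 12 have a row. The 0-16 week row in Table 3 is not the count, because the table note makes these rows dichotomous.

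**2. Whether other text supplies a method.** Analysis methods names none for counts, and the protocol's Statistical methods covers only continuous and binary outcomes. However, note 1 to Table 2 applies the mixed model to three other counts (swollen joints, tender joints, tophi), so the SAP already has a working convention. That model read at week 16 alone would give flares in weeks 8-16. Because it has a time-by-group term, the week 8 difference plus the week 16 difference is a linear contrast for the 16-week total.

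**3. What yes/no reporting loses.** Assume 9 of 30 patients with a flare in each arm.
- Risk difference 0, with 95% CI ±1.96 × √(2 × 0.3 × 0.7 / 30) = ±0.232.
- That result is the same whether total flares are 9 and 9 or 18 and 9. In the second case the rate ratio is 18/9 = 2.0, with Poisson 95% CI exp(0.693 ± 1.96 × √(1/18 + 1/9)) = 0.90 to 4.45.

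The yes/no rows do lose information, but even a doubling on these counts would give an interval that includes 1.

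**4. How far the choice of count method matters.** With equal true rates and variance k times the mean, a plain Poisson 95% CI excludes 1 with probability of about 2 × (1 − Φ(1.96/√k)). This is 0.110, 0.166 and 0.258 for k = 1.5, 2 and 3. Simulation with a mean of 1 flare and 30 per arm gave 0.105, 0.161 and 0.257. An interval adjusted for overdispersion stayed between 0.046 and 0.051. The SAP nowhere proposes a plain Poisson interval, so these figures describe a poor choice that nobody has made.

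**5. Missed week 16 count.** Assume a true ratio of 1, a constant rate, and m patients per arm seen only to week 8. The ratio of raw totals is (30 − 0.5·m_ID)/(30 − 0.5·m_CD):

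| Missing ID/CD | Raw totals |
|---|---|
| 6/0 | 27/30 = 0.90 |
| 6/2 | 27/29 = 0.93 |
| 6/6 | 27/27 = 1.00 |
| 2/6 | 29/27 = 1.07 |
| 0/6 | 30/27 = 1.11 |

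Dividing by observed weeks gives 1.00 in all five, but only because the rate was taken as constant. Suppose instead that 75% of flares fall in weeks 0-8, with a mean of 1 flare per patient and 6/0 missing. The ID arm then shows 24 + 6 × 0.75 = 28.5 flares over 24 × 16 + 6 × 8 = 432 weeks, against 30 over 480. Raw totals give 28.5/30 = 0.95, and rates give (28.5/432)/(30/480) = 1.06. The obvious remedy misses by about as much as the crude sum under the early-rise pattern that motivates the worry.

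**The case for a change.** The strongest case for a change is that the omission is plain, the data are already collected, and one row with one sentence would close it. Counts also carry more information than proportions. With an assumed rate ratio of 0.5, complete follow-up and control rates of 0.5 to 2.0 flares per patient, power is 0.34 to 0.87 for the count against 0.30 to 0.55 for any flare under Poisson. With negative binomial dispersion 1 it is 0.27 to 0.53 against 0.21 to 0.26. The reading of the text stands, and so does the loss of information.

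The consequences do not go as far as claimed. The shells are headed as a proposed outline, so a missing row does not remove an outcome that Section 6 lists. The nurse's count is not the only record. The protocol's Data monitoring section has adverse events recorded with date of onset, and its Harms section says flares are captured outside scheduled visits too. Those records use a broader definition than flares requiring treatment, so they may cover part of a missed period but do not replace the count. An early excess of patients with flares would still show in the first-8-weeks row. The harm signal rests on one surgical study, while the same protocol paragraph reports fewer flares in six of eight studies.

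**Conclusion.** The flare count lacks a row, a named method and a missed-visit rule. This is missing detail on an exploratory outcome and does not make any stated analysis wrong. The outcome is outside the hierarchical sequence. Other secondary rows in Table 2 show P-values as not applicable, and Table 3 has no P-value column, so a later choice of count model cannot produce a formal claim. The four tested endpoints and the any-flare proportions by period are unaffected. Analysts would normally supply totals and rates per arm or a standard count model, and the SAP's handling of joint and tophi counts already offers a fallback.

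The missed-visit effect is modest: 0.90 to 1.11 at the plan's own drop-out limit if all losses fall in one arm, and none if they balance. These figures assume a constant rate and that those patients were seen to week 8. If flare rates prove high and repeat flares common, the yes/no rows alone would understate them, and the listed count would then need to be reported with its method described. That is a matter for the report and does not require a change to the plan.
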